7.5.1.2.3 Causal Relationship/Definitions of Attribution

The assessment of the causal relationship between an AE and the administration of treatment is a clinical decision based on all available information. The assessment is based on the question whether there was a “reasonable causal relationship” to the study treatment in question.

An assessment of “not related” is defined as an adverse event being clearly not related or unlikely to be related. Adverse events can also be attributed as “possible/probable” defined as reasonably possible or likely to be related, or “definite” defined as the adverse event is clearly related.

Important factors to be considered in assessing the relationship of the AE to study treatment include:

- The temporal sequence from drug administration: The event should occur after the drug is given. The length of time from drug exposure to event should be evaluated in the clinical context of the event.
- Recovery on drug discontinuation (de-challenge), recurrence on drug re-introduction (re-challenge):
- Subject’s response after de-challenge or subjects response after re-challenge should be considered in the view of the usual clinical course of the event in question.
- Underlying, concomitant, intercurrent diseases:
Each event should be evaluated in the context of the natural history and course of the disease being treated and any other disease the subject may have.
- Concomitant medication or treatment:
The other drugs the subject is taking or the treatment the subject receives should be examined to determine whether any of them may be suspected to cause the event in question.
- The pharmacology and pharmacokinetics of the study treatment:
The pharmacokinetic properties (absorption, distribution, metabolism and excretion) of the study treatment, coupled with the individual subject’s pharmacodynamics should be considered.

7.5.1.2.4 Action taken with study treatment

Any action on study treatment to resolve the AE is to be documented using the categories listed below.

- Drug withdrawn
- Drug interrupted
- Not applicable
- Unknown

7.5.1.2.5 Outcome

The outcome of the AE is to be documented as follows:

- Recovered, without treatment
- Recovered, with treatment
- Still present, no treatment
- Still present, being treated
- Residual effect(s) present, no treatment
- Residual effect(s) present, being treated
- Subject died

7.5.1.3 Assessments and documentation of adverse events

The investigator has the obligation to report AEs. All non-serious events will be assessed and recorded during this trial from the baseline visit and until the end of study visit at week 16, whether believed to be related or unrelated to the treatment. The record will include clinical symptoms or final diagnosis when available, date of appearance, duration, severity, relationship to treatment and outcome. A record will also be kept of the action taken and the follow-up until resolution of the AE. For patients who stop study drug or withdraw before the end of the trial (16 week visit), AE will be re-assessed at 30 days after stopping the drug at a follow-up study visit. For all others, adverse events will be followed for 30 days, with patients contacted by phone call.

7.5.1.4 Reporting of serious adverse events

The definition of SAEs is given in Section 7.5.1.1.

Investigator's notification to the Safety Monitor

All SAEs occurring during the observation period defined in Section 7.5.1.3 must immediately (within 48 hours of the investigator's awareness) be reported to KAI, NIAMS and the internal Safety Officer. An SAE form must also be completed within 48 hours of the investigator awareness and forwarded. Each SAE must be followed up until resolution or stabilization by submission of updated reports.

Notification of the IRB

Notification of the University of Pittsburgh IRB about all relevant events (eg, SAEs, suspected, unexpected, serious adverse reactions [SUSARs]) will be performed according to IRB regulations.

7.5.1.5 Adverse events

7.5.1.6 Expected adverse events, and events of special safety interest

Common expected adverse events include: myalgias/artralgias (> 10%), diarrhea (5-14%), nasopharyngitis (4-13%), and dyspepsia (3-6%).

There are four significant adverse events associated with the use of atorvastatin which include 1) increase in fasting blood glucose in patients with diabetes mellitus; 2) hepatotoxicity; 3) rhabdomyolysis; and 4) the very rare event of immune-mediated necrotizing myopathy. Diabetes mellitus is an exclusion criteria for this study.

In regards to hepatotoxicity, elevated serum transaminases have been reported in as high as 2-3% of patients taking a higher dose of atorvastatin (80 mg once daily), although postmarketing reports of hepatic failure are rare. These will be monitored at baseline, week 8 and week 16. We will discontinue if hepatic enzymes are > three times the upper limit of normal.

Many patients receiving HMG-CoA reductase inhibitors experience myalgias, and this is an expected adverse event. Patients receiving HMG-CoA reductase inhibitors have developed rhabdomyolysis with acute renal failure and/or myopathy. This risk is dose-related and is increased with concurrent use of CYP3A4 inhibitors (eg, clarithromycin, protease inhibitors), fibric acid derivatives (eg, gemfibrozil), or niacin (doses ≥ 1 g/day) (see Drug Interactions), which will be monitored. Serum CPKs will be checked at baseline, week 8 and week 16. We will advise patients not to perform unusual or heavy bouts of exercise in the 24 hours before visits. We will discontinue in any patient in which CPK levels are markedly elevated (> 5 times ULN) or if myopathy is suspected/diagnosed. Patients will be instructed to report unexplained muscle pain, tenderness, weakness, or brown urine. If they develop any of these symptoms, they will return for an interval visit with repeat CPK and exam at that time.

Patients receiving HMB-CoA reductase inhibitors have also been rarely reported to develop an immune-mediated necrotizing myopathy (IMNM). IMNM presents as proximal muscle weakness with elevated CPK levels, which persists despite discontinuation of HMG-CoA reductase inhibitor therapy. Serum CPKs will be checked at baseline, week 8 and week 16. We will discontinue in any patient in which CPK levels are markedly elevated (>5 times ULN) or if myopathy is suspected/diagnosed.

Declaration of an event as serious should only occur when 1 or more of the serious criteria (as defined in Section 7.5.1.1) are applicable.

7.5.1.7 Expected adverse events

Expected adverse events are those listed as common (incidence > 2%) in patients treated with atorvastatin per the package insert. These include nasopharyngitis, arthralgia, diarrhea, extremity discomfort and urinary tract infection.

7.5.1.8 Unexpected adverse events

An adverse reaction is considered "unexpected" if it is not listed in the package insert for atorvastatin (please see Appendix I of the MOOP)

7.5.1.9 Pregnancies

A report of a confirmed pregnancy by serum testing will be submitted within the same timelines as an SAE, although a pregnancy per se is not considered an SAE.

For a study subject, the outcome of the pregnancy should be followed up to completion.

OTHER PROCEDURES AND VARIABLES

7.5.2 Pregnancy testing

Pregnancy testing is to be performed at the Baseline visit, Week 8 visit and Week 16 visit. In the event of pregnancy, a referral to a gynecologist for confirmation of pregnancy will be promptly organized. Further consequences with regard to ongoing participation in the study must be discussed with the patient.

Women of childbearing potential and non-vasectomized male participants must agree to use adequate contraception when sexually active. 'Adequate contraception' is defined as any combination of at least 2 effective methods of birth control, of which at least one is a physical barrier (e.g. condoms with hormonal contraception or implants or combined oral contraceptives, certain intrauterine devices). The exception will be women who have undergone tubal ligation and men who have undergone a vasectomy.

7.5.3 Vascular Assessments

Prior to beginning vascular testing, all patients will rest for 15 minutes in a quiet, dark and temperature-controlled room (set at 77 degrees Fahrenheit or warmer). Measurement of EndoPAT™, LSCI and brachial FMD will be performed simultaneously. Measurements will be obtained before and after vascular occlusion for all studies to assess endothelial dependent vasodilation. LSCI and brachial FMD will then be performed before and after administration of 0.4 mg of sublingual NTG to assess endothelial-independent vasodilation.

During the acclimation period a pneumatic cuff will be placed on the subject's right arm. Once the acclimation period has ended, a baseline pulse and flow measurements will then be obtained for 5 minutes for all modalities. Following this vaso-occlusion will be induced by inflating the pneumatic cuff to a pressure of 280 mmHg or 60 mmHg higher than systolic blood pressure (whichever was the highest), for 5 minutes. After 5 minutes the cuff will be rapidly deflated and measurements will be obtained for an additional 5 minutes. Subjects will then receive a single 0.4 mg sublingual spray of NTG. We will then obtain measurements as detailed in the individual vascular studies below over a period of 10 minutes.

7.5.4 EndoPAT

Measurement of microvascular endothelial function will be performed using Peripheral Arterial Tonometry (PAT) device (EndoPAT 2000, version 3.3.2, Hamar Medical, Caesavea, Israel). EndoPAT is a well-validated instrument¹⁸. After the vascular assessment acclimation period, probes will be placed on the tips of both index fingers. PAT signal measurement will be performed with the digital probe inflation pressure set at 10mmHg below the diastolic pressure or 70 mmHg (whichever is lowest) (17). Baseline pulse amplitude will be recorded bilaterally on tips of the index fingers for 5 minutes. Following vaso-occlusion on the right the cuff will be deflated and the PAT signal measurement was recorded for an additional 5 minutes. Mean PAT amplitudes will be measured 90 seconds after the occlusion for a duration of 60 seconds. Finally, the ratio of the post-to-pre occlusion PAT amplitude of the tested arm, divided by the post-to-pre occlusion ratio of the control arm, will be calculated as the Reactive Hyperemia Index (RHI).

7.5.5 Laser Speckle Contrast Imaging

For assessment of LSCI we will use the PerCam PSI system (Perimed AB, Jarfalla, Sweden), which produces a near infrared (780 nm) laser light. The backscattered light forms a random interference (speckle) pattern. Movement, as produced by circulating red blood cells, causes the speckle pattern intensity to change, thus allowing for quantification of flow. The PeriCam PSI system will be used with the camera placed 20 cm above the SSc patient's hand, which will be immobilized by a fluid support. A region of interest on the 2nd proximal metacarpophalangeal joint will be identified prior to beginning assessments. Baseline LSCI measurements will be obtained continuously beginning five minutes prior to vaso-occlusion until 5 minutes after NTG administration.

7.5.6 Brachial FMD

Brachial artery FMD will be performed using the GE Vivid 7 Dimension ultrasound (GE Vingmed Ultrasound A/S, Horten, Norway). Brachial artery diameter will be measured and calculated at baseline, 1, 2 and 3 minutes after reactive hyperemia induced by 5-minute pneumatic cuff occlusion, and then at 3, 5 and 10 minutes after NTG administration by means of averaging 3 measurements. FMD will be calculated as the percent change (%FMD) in brachial diameter from the resting state ($100 \times [\text{hyperemic diameter at selected time} - \text{resting diameter}] / \text{resting diameter}$) for reactive hyperemia. Similarly, vasodilator response to NTG will be expressed as percentage change (NTG%) in diameter between baseline and after NTG administration.

7.5.7 Exploratory Biomarkers

Samples for exploratory vascular biomarkers will be drawn at the baseline visit and week 16 (end of study). Serum biomarkers will include vascular soluble adhesion molecules (VCAM, ICAM, E-selectin and p-selectin), endothelin-1 (ET-1), vascular endothelial growth factor (VEGF), angiopoietin -1 and -2, inflammatory cytokines (C-reactive protein (CRP), serum complement levels, interleukin-2, interleukin-13) and circulating endothelial progenitor cells (cEPC).

We will also assess levels of nitrite and nitrotyrosine at baseline and week 16.

Circulating EPCs will be assessed at baseline and week 16.

7.5.8 Raynaud's attacks assessment

Raynaud's attacks will be assessed using the following individual outcome measures: in Raynaud's condition score and patient assessment of Raynaud's phenomenon using the VAS¹⁹

The Raynaud's condition score is a daily patient-assessment of Raynaud's phenomenon activity using a 0-10 ordinal scale. It incorporates the cumulative frequency, duration, severity and impact of Raynaud's phenomenon attacks, reflecting the overall degree that Raynaud's has affected use of the patient's hands¹⁹. The Raynaud's condition score, along with details of the frequency and duration of Raynaud's attacks, will be incorporated into the daily diary that subjects will be asked to complete for 1 week (7 days) at the time points shown below.

The patient and physician assessment assesses the severity of Raynaud's phenomenon in the past week using a 0-100 VAS.

7.5.9 Digital ulcer assessment

Digital ulcers are defined as a full thickness skin lesion with loss of epithelium. Ulcers should be > 3mm in maximal diameter. Healing is defined by re-epithelialization with loss of pain and exudate. Pitting scars and hyperkeratotic lesions are always excluded. Also, eschar is not considered as DU.

Digital ulcer will be assessed by the following methods:

- Visual analog score for patient-reported severity of digital ulcers
- Ulcer count:
 - Total ulcer counts
 - Distal counts: distal (fingertip) – any ulcer including skin area distal to proximal interphalangeal (PIP) joint
- Non-ischemic ulcers over the PIP and MCP will also be evaluated for healing as secondary outcomes

7.5.10 Patient-Reported Outcomes (PROs) / Health-Related Quality of Life (HRQoL) questionnaires

Two patient-reported outcomes (PROs)—the SHAQ and PROMIS-29—will be completed by all subjects in the study. In addition, a global for patient and physician should be considered.

Scleroderma Health Assessment Questionnaire (SHAQ)

The SHAQ consists of 8 domains from the Health Assessment Questionnaire disability index (HAQ-DI), a HRQoL instrument that measures self-reported function in 8 domains of activity in 20 weighted responses and a VAS of pain experienced in the past week. It additionally measures 5 domains specific to scleroderma using a continuous VAS: Raynaud's phenomenon, digital tip ulcers, lung symptoms, gastrointestinal symptoms, and a global patient assessment⁷. The VAS subscales of the SHAQ were shown to be significantly correlated with objective parameters,⁷ and was responsive to change in a cohort and in a Raynaud's phenomenon trial in SSc.^{7,20} The SHAQ requires approximately 5 minutes to complete.

Patient-Reported Outcomes Measurement Information System (PROMIS)-29

The PROMIS-29 is a validated instrument to measure the health status of SSc patients, demonstrating moderate to high correlation with other instruments validated in SSc, including the SF-36 physical component score and HAQ-DI.²¹ It incorporates 7 core domains from the PROMIS questionnaire, which specifically relate to physical, mental, and social health aspects of chronic illness: pain, fatigue, depression, anxiety, sleep, and physical function, as well as one 11-point rating scale for pain intensity.²¹ It contains 8 items with 29 weighted responses in total, and requires approximately 5 minutes to complete.

Frequency of all PROs: Baseline (Visit 1, Day 0), Visit 5 (week 8), Visit 6 (week 10) and Visit 8 (week 16)

8. Statistical methods

8.1 General considerations

An intention to treat analysis will be performed including all who receive one dose of drug. Initial analysis will describe the baseline population, sociodemographic and clinical characteristics, and compare by treatment group. Means of continuous measures will be conducted using a t-test or Wilcoxon test and discrete measures compared with a chi-square test. The goal of all trial analyses is to provide effect size estimates for design of a later phase 3 clinical trial of statin therapy in early diffuse SSc, if deemed appropriate. If not mentioned otherwise, all statistical tests will be performed with a type I two-sided error rate of $\alpha=5\%$.

8.2 Statistical and analytical plans

8.2.1 Demographic and other baseline characteristics

Demographic variables and baseline characteristics will be summarized by treatment group.

8.2.2 Efficacy

The primary outcome of interest is the change in the EndoPAT measured RHI between baseline and week 16 between the atorvastatin and placebo group. A t-test will be used to compare the mean levels between the two groups. If differences in baseline characteristics across treatment groups are identified, multivariable linear regression models will be used to estimate the independent effect of treatment after controlling for the possible confounding variables.

The secondary outcomes of interest include the following:

- 1) Change in RCS
- 2) Change in Raynaud VAS
- 3) Change in reperfusion peak between the atorvastatin and placebo groups.
- 4) Change in reperfusion nadir between the atorvastatin and placebo groups.
- 5) Change in brachial FMD between baseline and week 16 between the atorvastatin and placebo group.

A t-test will be used to compare the mean change in RCS and Raynaud VAS between weeks 16 and baseline in the placebo and atorvastatin therapy groups. The means of reperfusion peak and nadir between groups will be calculated and a 95% confidence interval of the difference between means generated. A t-test will be used to compare the mean change in brachial FMD between baseline and week 16 between the two treatment groups.

For all of the above, assumptions of all tests (e.g., normality of residuals) will be evaluated. If violations are identified, transformations will be investigated. If adequate transformations cannot be identified, then nonparametric methods will be used.

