Plan for statistical analysis	An intention to treat analysis will be performed including all who receive one dose of drug. Initial analysis will describe the baseline population, sociodemographic and clinical characteristics, and compare by treatment group. Means of continuous measures will be conducted using a t-test or Wilcoxon test and discrete measures compared with a chi-square test. The goal of all trial analyses is to provide effect size estimates for design of a later phase 3 clinical trial for statin therapy in early diffuse SSc. The means of EndoPAT for the two groups will be calculated and a 95% confidence interval of the difference of the means will be generated. A t-test will be used to compare the mean levels between the two groups.

Table of contents

1. Introduction	7
1.1 Background	7
1.1.1 Scleroderma (systemic sclerosis)	7
1.1.2 Atorvastatin	8
1.1.3 Mechanism of Action	8
1.2 Rationale of the study	8
2. Study objectives	9
3. Investigators and other study personnel	9
4. Study design	10
4.1 Design overview	10
5. Study population	11
5.1 Eligibility	11
5.1.1 Inclusion criteria	11
5.1.2 Exclusion Criteria	12
5.1.3 Justification of selection criteria	13
5.2 Withdrawal of subjects from study	13
5.2.1 Withdrawal	13
5.2.2 Replacement	14
5.3 Subject identification	14
6. Treatment	14
6.1 Treatments to be administered	14
6.2 Identity of study treatment	14
6.3 Treatment assignment	14
6.4 Dosage and administration	14
6.4.1 Selection of doses in the study	14
6.5 Blinding	15
6.6 Drug logistics and accountability	15
6.7 Post-study therapy	15
6.8 Prior and concomitant therapy	15
7. Procedures and variables	17
7.1 Schedule of procedures	17
7.1.1 Tabulated overview	18
7.1.2 Timing of assessments	19
7.1.2.1 Visit 0 – Screening	19
7.1.2.2 Visit 1 – Baseline (Day 0, Week 0)	19
7.1.2.3 Visit 2: 8 weeks	20
7.1.2.4 Visit 3: 16 weeks (end of study)	20
7.1.2.5 Premature discontinuation of study drug treatment	21
7.2 Population characteristics	21
7.2.1 Demographic	21
7.2.2 Medical history	21
7.3 Efficacy	21

7.4	Pharmacokinetics / pharmacodynamics	22
7.5	Safety	22
7.5.1	Adverse events.....	22
7.5.1.1	Definitions.....	22
7.5.1.2	Classifications for adverse event assessment.....	23
7.5.1.2.1	Seriousness.....	23
7.5.1.2.2	Intensity.....	23
7.5.1.2.3	Causal relationship.....	24
7.5.1.2.4	Action taken with study treatment	24
7.5.1.2.5	Outcome	25
7.5.1.3	Assessments and documentation of adverse events	25
7.5.1.4	Reporting of serious adverse events	25

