8.4 Determination of sample size

This is a pilot study. With a total sample of 30 participants (15 per treatment group), and to produce a 95% confidence interval of the difference in means between the two treatment groups, the width of the confidence interval would be +/- 0.374.

9. Data handling and quality assurance

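### Section 8.2.2 does not pre-specify baseline RHI as a covariate and leaves its conditional regression undefined; a baseline-RHI ANCOVA would give one defined, usually more precise estimate

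*Combined protocol and SAP*

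**What the plan says.** Section 8.2.2 defines the endpoint: "The primary outcome of interest is the change in the EndoPAT measured RHI between baseline and week 16". The primary test follows: "A t-test will be used to compare the mean levels between the two groups". For two secondary outcomes the same section is more specific: "A t-test will be used to compare the mean change in RCS and Raynaud VAS between weeks 16 and baseline". It words brachial FMD as a mean change too.

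Adjustment is conditional: "If differences in baseline characteristics across treatment groups are identified, multivariable linear regression models will be used to estimate the independent effect of treatment". The covariates are described only as possible confounders. Where assumptions fail and transformation does not help, the section adds: "If adequate transformations cannot be identified, then nonparametric methods will be used".

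The synopsis gives only the unadjusted comparison: "The means of EndoPAT for the two groups will be calculated and a 95% confidence interval of the difference of the means", followed by a t-test. Section 8.1 sets the default that "all statistical tests will be performed with a type I two-sided error rate of" 5%, and says the aim of all analyses is effect size estimates for a later phase 3 trial. Section 8.4 gives the planned precision: "the width of the confidence interval would be +/- 0.374".

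**The concern.** EndoPAT is done at baseline and week 16 (schedule in 7.1.1), so baseline RHI will be in hand. Section 6.3 describes 1:1 randomisation and names no stratification factor, so chance imbalance in baseline RHI among 30 patients is left to the analysis.

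The plan leaves three things open:

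- what counts as an identified difference. The 5% default in 8.1 is a natural reading, but 8.2.2 does not state it;
- which covariates enter the model;
- whether the regression replaces the t-test or supplements it.

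The wording of the primary test also allows a comparison of week 16 levels rather than of changes.

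The deliverable is an effect size. If baseline RHI differs by chance, the change t-test and an adjusted model give different effect sizes, and the plan does not say which one is used to design phase 3. Not using baseline RHI as a covariate also usually widens the interval.

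**Working it through.** **Inputs from the documents.** 15 per arm and ±0.374 (8.4); two-sided 5% (8.1); endpoint and test (8.2.2).

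**Assumptions.** The SD; the correlation r between baseline and week 16 RHI; normal data with equal SD at both visits; no treatment effect; and, where a trigger is needed, p<0.05 on baseline RHI.

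**1. The plan's own figure.** Half-width = t(0.975, 28) × SD × √(2/15). With SD 0.50: 2.048 × 0.50 × 0.3651 = 0.374. So 0.374 matches an SD of 0.50. The documents do not say whether that is the SD of change or of a single RHI value, so both readings are shown.

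**2. Precision.** If a single RHI value has variance σ², the change has variance 2σ²(1−r), and week 16 RHI given baseline has σ²(1−r²). The ratio is (1+r)/2, or 0.65, 0.75, 0.85 and 0.925 at r = 0.3, 0.5, 0.7 and 0.85. At 15 per arm, allowing for the lost degree of freedom and expected chance imbalance, with SD of change 0.50:

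half-width = t(0.975, 27) × 0.50 × √((1+r)/2) × √(2/15) × √(1+1/26)

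At r = 0.5: 2.052 × 0.50 × 0.866 × 0.3651 × 1.019 = 0.331.

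Mean half-widths from 60,000 simulated trials per setting are below. They run just under the formula values because a sample SD averages slightly less than the true SD.

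| r | SD of change 0.50: change t-test | ANCOVA | SD of level 0.50: week 16 t-test | change t-test | ANCOVA |
|---|---|---|---|---|---|
| 0.3 | 0.371 | 0.305 | 0.371 | 0.439 | 0.361 |
| 0.5 | 0.371 | 0.328 | 0.371 | 0.371 | 0.327 |
| 0.7 | 0.371 | 0.349 | 0.371 | 0.287 | 0.270 |
| 0.85 | 0.371 | 0.364 | 0.371 | 0.203 | 0.199 |

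Under the first reading ANCOVA gives 0.369 at r = 0.9 and 0.374 at r = 0.95, so the gain disappears at very high correlation.

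**3. How far the two estimates can part.** Let D0 and D16 be the between-arm differences at baseline and week 16, and b the within-arm slope. The change estimate is D16 − D0 and the ANCOVA estimate is D16 − b·D0, so the gap is |1−b| × |D0|. At r = 0.5 under the first reading, the SD of level is 0.50/√(2 × 0.5) = 0.50 and b is about 0.5. The p<0.05 trigger then needs |D0| of about 0.374, so the gap starts near 0.5 × 0.374 = 0.187.

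| Median gap in RHI units | r = 0.3 | r = 0.5 | r = 0.7 |
|---|---|---|---|
| Trigger fires (5% of trials), SD of change 0.50 | 0.24 | 0.20 | 0.16 |
| Trigger fires, SD of level 0.50 | 0.28 | 0.20 | 0.12 |
| All trials, SD of change 0.50 | 0.07 | 0.06 | 0.04 |

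Against the planned half-width, the first row runs from 0.16/0.374 = 0.43 to 0.24/0.374 = 0.64, and the last from 0.04/0.374 = 0.11 to 0.07/0.374 = 0.19.

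**4. Coverage when baseline means differ by more than 0.5 SD.** This happens in about 17% of trials (0.5/0.3651 = 1.37 standard errors, two-sided). Coverage of the 95% CI, SD of change 0.50:

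| Analysis | r = 0.3 | r = 0.5 | r = 0.7 |
|---|---|---|---|
| Change t-test alone | 86% | 88% | 91% |
| ANCOVA only if baseline RHI p<0.05, otherwise t-test | 91% | 92% | 93% |
| ANCOVA always | about 95% | about 95% | about 95% |

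The p<0.05 trigger fires in only 29% of these imbalanced trials. With p<0.20 it fires in about 93% of them and conditional coverage is about 94–95%. The result therefore depends on the threshold the plan omits.

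**5. Overall error rates.** Over all trials the change t-test covers 95%. The strict p<0.05 rule has a type I error of 4.1–4.7% at r = 0.3 to 0.7, so it causes no inflation.

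**The case against.** The strongest reply is that nothing here is invalid. The unadjusted t-test has correct overall coverage, and a strict trigger rule does not inflate type I error. The trial is a pilot. Baseline RHI can be read as a baseline characteristic, so the regression clause already permits adjusting for it, and the clause can be read as supplying the effect estimate once triggered. The benefit depends on an r that no document gives. The coverage figures for the rule depend on an assumed p<0.05 trigger, and a looser one largely removes the shortfall. The larger gaps arise in only 5% of trials.

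Much of this stands. The conditional figures are illustrative, the precision gain is small at high r, and this is not an error-rate problem. But each reading that rescues the clause has to be supplied by the reader: a threshold, baseline RHI as a covariate, replacement rather than supplement. Reporting whichever of the change t-test and ANCOVA is significant, which the plan does not rule out, gives a type I error of 6.9–7.7% at r = 0.3 to 0.7 in 40,000 trials per setting. Being a pilot does not help either, because estimation is its stated purpose.

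Two further objections are fair. The retained transformation and nonparametric steps still leave some data-driven choice. No calculation was made for the secondary outcomes, so extending the model to them rests on the general argument and on consistency.

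**Conclusion.** The concern holds, as a change that should be made rather than a flaw that invalidates the trial. Baseline RHI is not pre-specified, and the trigger, covariates and status of the regression are undefined; none of this depends on any assumed value. The size of the gain does. If the SD of change is 0.50, the mean half-width narrows by about 18%, 12% and 6% at r = 0.3, 0.5 and 0.7 (1 − 0.305/0.371, 1 − 0.328/0.371, 1 − 0.349/0.371), by 2% at r = 0.85, and not at all by r = 0.95. The ambiguity about which estimate to carry forward is modest in most trials. It becomes material when baseline RHI happens to differ.

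**What to change.** - **Primary analysis (8.2.2 and synopsis).** Specify an ANCOVA of RHI at week 16 on treatment, with baseline RHI as the one pre-specified covariate, and report the adjusted mean difference with its 95% CI. Using change as the outcome in this model gives the same treatment estimate, so this also settles the wording about levels versus change.
- **Status of other adjustment.** State that any model adjusting for observed baseline imbalance is a sensitivity analysis and does not replace the primary estimate.
- **Assumption checks.** Keep the planned checks, transformations and nonparametric fallback, applied to the ANCOVA residuals. Say that any transformation is made to RHI itself at both visits, since a change can be negative, and name the fallback method.
- **Section 8.4.** State that 0.374 is the unadjusted figure and whether its SD is of change or of level.
- **Secondary outcomes.** Use the same baseline-adjusted model for RCS, Raynaud VAS, reperfusion peak and nadir, and brachial FMD.

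The cost is wording in 8.2.2 and the synopsis, a clarifying sentence in 8.4, and one degree of freedom (27 instead of 28). No new data are needed.
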